Official Title: Diamox/Aldactone to Increase the URinary Excretion of Sodium: an Investigational Study in Congestive Heart Failure

NCT01973335

Date: August 27, 2015

1. Background

Aging of the population and prolongation of the lives of cardiac patients by modern therapeutic innovations have led to an increased incidence of congestive heart failure (CHF).¹ During the last two decades, important progress has been made in the treatment of ambulatory CHF patients with reduced ejection fraction. Renin-angiotensin system blockers, β -blockers, mineralocorticoid receptor antagonists (MRA), ivabradine and cardiac resynchronization therapy have all demonstrated to reduce morbidity and/or mortality in ambulatory CHF patients.²⁻¹⁷ Despite these important advances, many patients are still hospitalized frequently with signs and symptoms of systemic congestion, which is associated with worse outcome.¹⁸ Treatment in these cases mainly focuses on symptomatic relief through administration of diuretics, although clear evidence on the optimal agent, dosing schedule, and administration route is lacking.

Coexisting renal dysfunction often complicates decongestive treatment and worsening renal function (WRF), often defined as a 0.3 mg/dL rise in serum creatinine (Cr), is a common finding in this context.¹⁹ However, the prognostic impact of WRF, defined as Cr change is unsure as it might be associated with worse, neutral or even better outcome.²⁰⁻²² In contrast, persistent congestion, as a reflection of the inability of the kidneys to preserve sodium homeostasis, has been more consistently associated with higher mortality and more frequent readmissions in CHF.²³ This suggests that achieving a negative sodium balance might be an attractive treatment target in heart failure.

Loop diuretics are by far the most commonly used diuretic agents to achieve a negative sodium balance in acute decompensated heart failure (ADHF). Especially in diuretic-naïve patients, they are often very effective to relief dyspnea and congestive symptoms. However, in the recent Diuretic Optimization Strategies Evaluation (DOSE) trial, no differences in patients' global assessment of symptoms or change in renal function were observed when loop diuretics were administered by bolus as compared with continuous

infusion or at high versus low dose during a hospitalization for ADHF, with high dose therapy currently considered as usual care by most clinicians.²⁴ Importantly, there are several reasons why loop diuretics might be less effective or even harmful in CHF. First, loop diuretics directly stimulate renin production by inhibiting the $\text{Na}^+/\text{K}^+/\text{2Cl}^-$ -cotransporter on the luminal side of the macula densa, which depletes intracellular chloride levels in the macula densa. The consequence is an increased COX-2 and NOS I activity in macula densa cells, leading to paracrine PGE_2 and NO secretion.²⁵ Both PGE_2 and NO work in concert to stimulate renin release by granulosa cells of the afferent arteriole and further detrimental activation of the renin-angiotensin-aldosterone axis. Second, impaired secretion of loop diuretics in the proximal tubules of CHF patients, especially when there is concomitant renal dysfunction, results in lower concentrations at the place where these agents act – the luminal side of the thick ascending limb of Henle’s loop (TAL). Third, increased sodium reabsorption in the proximal tubules might result in less sodium offered to the TAL, especially if glomerular filtration is concomitantly impaired, hampering the efficacy of loop diuretics. As a result, physicians often use combination therapies of different acting diuretic agents in order to increase the overall diuretic effect.

From a pathophysiological point of view, targeting sodium reabsorption in the proximal tubules has several potential benefits in CHF. First, it is the place where most sodium is reabsorbed, especially in ADHF. Second, greater delivery of chloride to macula densa cells will decrease renin production, ceasing neurohumoral activation. Third, endogenous natriuretic peptides (acting in the distal nephron) will possibly regain their effects. The carbonic anhydrase inhibitor acetazolamide (Diamox®), which is approved for the treatment of mountain sickness and is used to increase the diuretic efficacy of loop diuretics in patients with therapy-refractory congestion, inhibits sodium reabsorption in the proximal tubules. Remarkably, in a small study of 9 patients with advanced CHF and diuretic resistance, therapy with acetazolamide was able to elicit potent diuresis.²⁶ Despite this

promising case series and the pathophysiological rationale for inhibition of proximal sodium reabsorption in ADHF, acetazolamide is now a largely forgotten diuretic.

MRA have an established role in the treatment of chronic CHF.^{11, 12} However there are remarkable few data on their use in patients who present with ADHF. Nevertheless, in this context with frequent use of potassium wasting diuretics, they might be of particular interest to prevent occurrence of hypokalemia, which has been associated with a worse prognosis.²⁷ Moreover, by inhibiting distal tubular sodium reabsorption and counteracting aldosterone breakthrough, MRA might improve the natriuretic efficiency of loop diuretics.

2. Study Hypotheses

1. Combination therapy with acetazolamide improves loop diuretic efficacy to induce natriuresis in ADHF patients, allowing for a lower dose of the latter medication and potentially less adverse events such as worsening renal function.
2. Combination therapy with acetazolamide and low-dose loop diuretics leads to less pronounced neurohumoral activation compared to treatment with high-dose loop diuretics in ADHF patients.
3. Upfront therapy with MRA is safe in patients presenting with ADHF and lowers the incidence of hypokalemia and the need for potassium supplementation, without causing a higher incidence of hyperkalemia.
4. Combination diuretic therapy with acetazolamide and/or upfront spironolactone will lead to improved clinical outcome (less heart failure rehospitalizations and lower all-cause mortality).

3. Study Protocol

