3.1. Study design

Randomized clinical trial with factorial 2x2 design, 2 treatment arms, and 4 groups (n=20 each):

- Arm 1: Acetazolamide + low-dose loop diuretics versus high-dose loop diuretics (=standard of care)
 - ➔ Triple blinded to treatment allocation (patient, treating physician and investigator blinded)
- Arm 2: Upfront versus discharge spironolactone
 - ➔ Treating physician and investigator blinded to treatment allocation. Patient not blinded to treatment allocation because no matching placebo will be provided due to logistic constraints.

Consecutive patients, presenting with ADHF at different Belgian hospitals will be screened by staff members, cardiology fellows, a study nurse and the cardiology Ph.D. fellows. All those people will be able to login via the website www.hartcentrumlimburg.be, where they can print the case report form and informed consent of the study and will receive the randomization number by a computer algorithm with blocks of 4.

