3.5.2. Primary study end-point for spironolactone arm

Incidence of hypo- (serum potassium <3.5mmol/L or need for oral/intravenous potassium supplements) or hyperkalemia (serum potassium >5.0mmol/L) during the entire 72 h interval after randomization.

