3.6. Statistical analysis

Continuous variables will be expressed as mean \pm standard deviation when normally distributed and as median (interquartile range) in case of a non-normal distribution. Normality will be assessed by the Shapiro-Wilk statistic. The independent-samples Student's *t*-test and Mann-Whitney *U* test will be used as indicated to compare between groups. Categorical variables will be expressed as percentages and compared using Fisher's exact test or Pearson's χ^2 -test in case of a non-binary response. Statistical significance will always be set at a 2-tailed probability level of <0.05 . All statistics will be performed using IBM SPSS® (Chicago, Illinois, USA) (version 22.0 for Mac).

4. Potential adverse events

- Metabolic acidosis is the only agent-specific adverse event that might be expected from treatment with acetazolamide. Serum bicarbonate is monitored daily. If serum bicarbonate <22 meq/L, substitution with oral NaHCO_3 will be provided.
- Hyperkalemia might be expected as a potential adverse event of spironolactone, but this medication will be withheld when serum potassium levels are >5.0 mmol/L and serum potassium levels are monitored daily throughout the study.

5. References

- american heart association. *Circulation*. 2013;127:e6-e245
2. Effect of enalapril on survival in patients with reduced left ventricular ejection fractions and congestive heart failure. The solvd investigators. *The New England journal of medicine*. 1991;325:293-302

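### Hypothesis 3 claims no higher incidence of hyperkalemia with upfront spironolactone, but section 3.6 gives only two-sided tests of difference and no criterion that could support a no-excess claim

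*Combined protocol and SAP*

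**What the plan says.** Hypothesis 3 in section 2 has two parts. The first is directional: "Upfront therapy with MRA is safe in patients presenting with ADHF and lowers the incidence of hypokalemia", along with less need for potassium supplements. The second is a no-excess claim, that this happens "without causing a higher incidence of hyperkalemia".

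Hyperkalemia is also part of the primary end-point of the spironolactone comparison. Section 3.5.2 counts hypokalemia (low potassium or need for supplements) "or hyperkalemia (serum potassium >5.0mmol/L) during the entire 72 h interval after randomization". The text does not say whether this is one composite or two separate outcomes.

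Section 3.1 gives the size: "Randomized clinical trial with factorial 2x2 design, 2 treatment arms, and 4 groups (n=20 each"). The contrast is "Arm 2: Upfront versus discharge spironolactone".

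Section 3.6 is the whole statistical plan. For this kind of outcome it says: "Categorical variables will be expressed as percentages and compared using Fisher's exact test", with Pearson's chi-square for non-binary responses. It adds: "Statistical significance will always be set at a 2-tailed probability level of <0.05". It contains no interval for a between-group difference, no margin, no assumed event rate, no power calculation, and no statement of what result would support the second part of hypothesis 3.

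**The concern.** A two-sided test of difference suits the hypokalemia part of hypothesis 3, where the aim is to show a reduction. It does not suit the hyperkalemia part. A significant excess could refute that claim, but a non-significant result shows only that a difference was not demonstrated. So no result of the planned analysis can support the claim.

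This matters because section 4 itself names hyperkalemia as an adverse event that may be expected from spironolactone, and section 1 says that data on these drugs in acute decompensated heart failure are few. A safety statement from this trial would therefore carry weight. With percentages and a p-value as the only planned output, a reader could not see how large an increase the data still allow.

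**Working it through.** **Inputs from the protocol.** Four groups of 20 (section 3.1); Fisher's exact test, two-sided 0.05 (section 3.6); hyperkalemia defined as potassium above 5.0 mmol/L within 72 h (section 3.5.2).

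**Inputs inferred or assumed.** Pooling over the acetazolamide factor gives 2 x 20 = 40 per side; section 3.6 does not state this. No event rate is given, so control rates of 5, 10, 15 and 20% are assumed. No margin is given. The protocol has no sample-size figure to reproduce, because n=20 is stated without a derivation.

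**Step 1: chance of a non-significant result when there is a true increase.** For true rates p0 and p1, sum Bin(c; 40, p0) x Bin(t; 40, p1) over all pairs of counts (c, t) with Fisher p >= 0.05.

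| True rates | Power | Non-significant |
|---|---|---|
| 5% v 10% (doubling) | 4% | 96% |
| 10% v 20% (doubling) | 16% | 84% |
| 15% v 30% (doubling) | 28% | 72% |
| 20% v 40% (doubling) | 41% | 59% |
| 5% v 15% (tripling) | 18% | 82% |
| 10% v 30% (tripling) | 53% | 47% |

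If single groups of 20 were compared instead, power for 10% v 20% would fall to 7%.

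**Step 2: what a non-significant result leaves open.** Newcombe's interval for the difference d = p1 - p0 uses the Wilson limits (l, u) of each proportion:

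- lower limit = d - sqrt[(p1 - l1)^2 + (u0 - p0)^2]
- upper limit = d + sqrt[(u1 - p1)^2 + (p0 - l0)^2]

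*Equal counts, 4/40 v 4/40.* The Wilson limits for 10% are 3.96% and 23.05%. Upper limit = 0 + sqrt(13.05^2 + 6.04^2) = +14.4 points.

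*Control 4/40 v upfront 8/40.* Fisher p = 0.35; interval -6 to +26 points.

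*Control 2/40 v upfront 8/40.* Fisher p = 0.087, so not significant; 9/40 is the first count flagged against 2/40 (p = 0.048). The Wilson limits are 1.38% to 16.50% and 10.50% to 34.76%.
- Lower limit = 15 - sqrt(9.50^2 + 11.50^2) = +0.1 points.
- Upper limit = 15 + sqrt(14.76^2 + 3.62^2) = +30.2 points.

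**Step 3: what margin 40 v 40 could support.** With equal true rates p, one-sided 0.025 and 80% power, the smallest testable margin is (1.960 + 0.842) x sqrt[2p(1 - p)/40].

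| Assumed rate | sqrt term | Smallest margin | Power for a 10-point margin |
|---|---|---|---|
| 5% | 0.0487 | 13.7 points | 54% |
| 10% | 0.0671 | 18.8 points | 32% |
| 15% | 0.0798 | 22.4 points | 24% |
| 20% | 0.0894 | 25.1 points | 20% |

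For a 10-point margin, 80% power would need 75, 142, 201 and 252 per side respectively.

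**The case against.** The strongest reply is that the protocol nowhere says that a non-significant p-value will be read as safety. That is correct. A reader might infer such a rule from hypothesis 3 and section 3.6 taken together, but no passage states it. What the documents show is the absence of any criterion, not the adoption of a wrong one.

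A second reply is that the size of the problem depends on assumptions. This also stands in part. A reader might conclude that the test would usually miss a tripling of hyperkalemia. That holds from an assumed 5% control rate but not from 10%, where a tripling is detected slightly more often than missed. The 40 v 40 base is inferred. So is a separate test of hyperkalemia: if section 3.5.2 defines one composite, the figures in step 1 do not describe the planned test. That reading does not rescue the hypothesis, because hyperkalemia would then have no comparison of its own, and fewer hypokalemia events could offset an excess.

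A third reply is that sections 3.3.4 and 4 provide for daily potassium monitoring and for withholding spironolactone on raised potassium, so patient protection does not depend on this test. That is fair, but it does not supply evidence for the claim.

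Finally, adding an interval beside Fisher's test can give conflicting signals. At 2/40 v 8/40 the Newcombe interval just excludes zero while Fisher's p is 0.087. The revised plan must say which one governs.

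**Conclusion.** The concern holds in a limited form. The hyperkalemia and safety part of hypothesis 3 has no analysis in section 3.6 that could support it, and the only apparent basis, a non-significant p-value, would not do so. This follows from the text and needs no assumed figures.

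The size does rest on assumptions: 40 per side, hyperkalemia compared on its own, and control rates of 5-20%. On those, a true doubling would be non-significant in about 59-96% of trials, and identical observed counts of 4/40 could not exclude an excess of 14 points. The documents do not support the stronger statements that the sponsor plans to treat non-significance as safety, or that a tripling would be missed at every plausible rate. The hypokalemia part of hypothesis 3 is not affected.

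**What to change.** In section 3.6, report hyperkalemia (potassium above 5.0 mmol/L within 72 h) on its own, by spironolactone allocation pooled over the acetazolamide factor, as a risk difference with a two-sided 95% Newcombe interval. Name that interval as the basis for the hyperkalemia conclusion, so that it does not compete with the Fisher p-value.

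In section 2, reword the hyperkalemia part of hypothesis 3 to say that the trial will estimate the difference in hyperkalemia, and state that a non-significant p-value will not be read as evidence of safety.

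Keep the no-excess wording only if the sponsor fixes a margin before unblinding and requires the upper limit to lie below it. Step 3 shows that only wide margins are within reach at this size, so rewording is the realistic route.

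The cost is limited to wording and reporting. Allocation, treatment, sample size and data collection are unchanged, since serum potassium is already monitored daily. The downside is that the stated safety claim becomes less favourable.

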3.1. Study design

Randomized clinical trial with factorial 2x2 design, 2 treatment arms, and 4 groups (n=20 each):

- Arm 1: Acetazolamide + low-dose loop diuretics versus high-dose loop diuretics (=standard of care)
 - ➔ Triple blinded to treatment allocation (patient, treating physician and investigator blinded)
- Arm 2: Upfront versus discharge spironolactone
 - ➔ Treating physician and investigator blinded to treatment allocation. Patient not blinded to treatment allocation because no matching placebo will be provided due to logistic constraints.

Consecutive patients, presenting with ADHF at different Belgian hospitals will be screened by staff members, cardiology fellows, a study nurse and the cardiology Ph.D. fellows. All those people will be able to login via the website www.hartcentrumlimburg.be, where they can print the case report form and informed consent of the study and will receive the randomization number by a computer algorithm with blocks of 4.

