3.3.3. Arm 2, control group: Discharge spironolactone

This group will receive no active treatment. No placebo will be provided either due to logistic constraints. As instructed by the guidelines, addition of a MRA to maintenance therapy will be recommended upon discharge from the hospital.

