3.3.4. Arm 2, treatment group: Upfront spironolactone

This group will receive oral spironolactone 25 mg immediately after randomization and subsequently each day in the morning (10u00) provided serum potassium levels are <5.0 mmol/L. If no contraindications emerge during hospitalization, spironolactone will be added to the maintenance therapy of the patient upon hospital discharge.

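### One published block size of 4, with no spironolactone placebo, leaves up to a third of Arm 2 allocations deducible by anyone who sees the earlier allocations in the block

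*Combined protocol and SAP*

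**What the plan says.** Section 3.1 of the combined protocol and SAP describes a 2x2 factorial trial with four groups of 20. Patients "will be screened by staff members, cardiology fellows, a study nurse and the cardiology Ph.D. fellows", at more than one Belgian hospital. The same people log in to the trial website and "will receive the randomization number by a computer algorithm with blocks of 4". No variation in block size, no stratification by hospital and no central or per-hospital structure of the list is stated.

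For Arm 2, section 3.1 says of the staff: "Treating physician and investigator blinded to treatment allocation". It says of the patient: "Patient not blinded to treatment allocation because no matching placebo will be provided due to logistic constraints". Section 3.3.3 says of the control group: "This group will receive no active treatment. No placebo will be provided either due to logistic constraints". Section 3.3.4 says of the other group: "This group will receive oral spironolactone 25 mg immediately after randomization and subsequently each day in the morning (10u00". The plan does not describe who hands out the tablets, how the blinded staff are kept from seeing them, or whether the people who screen are also the blinded physicians and investigators.

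**The concern.** Four is the smallest block that can hold four equally sized groups, so every complete block contains two upfront and two discharge patients. Once two patients of one kind have been seen, the rest of the block is known. The size stands in the protocol, and one Arm 2 group takes a tablet while the other takes nothing, so allocations may become known on the ward despite the declared blinding.

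A screener who can anticipate the next allocation may, even without intending it, decide not to approach a particular patient. The Arm 2 primary end-point (section 3.5.2) is hypo- or hyperkalemia within 72 h, which plausibly depends on baseline potassium and renal function. Section 3.2.2 has no potassium exclusion, so patients with an abnormal value are eligible and passing one over would breach no listed criterion. Section 3.6 plans only unadjusted group comparisons, with 2 × 20 = 40 patients per Arm 2 level, so any imbalance created by selection would carry straight into the result.

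**Working it through.** The plan gives no predictability figure, so there is none to reproduce.

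**Inputs.** From section 3.1: block size 4; four groups of 20, hence 80 patients and 20 blocks. Equal allocation is inferred from the equal group sizes. Assumed: the observer knows the block size and where blocks start, and sees either all earlier Arm 2 allocations in the block or a share p of them.

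**Full sight (p = 1).** Project a block on its Arm 2 labels, two upfront and two discharge. The result is the same whether the four groups are permuted jointly or Arm 2 is blocked 2+2.

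| Position | Probability that it is certain | Best-guess success |
|---|---|---|
| 1 | 0 | 1/2 |
| 2 | 0 | 2/3 |
| 3 | 1/3 (first two alike) | 1/3 × 1 + 2/3 × 1/2 = 2/3 |
| 4 | 1 | 1 |

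Certain share: (0 + 0 + 1/3 + 1)/4 = 1/3, or 80/3 ≈ 26.7 of 80 patients. Best-guess success: (1/2 + 2/3 + 2/3 + 1)/4 = 70.8%. A person who knows only the Arm 2 labels still guesses the Arm 1 label at 50%.

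**Partial sight of a central list.** Each earlier patient is seen with probability p. Position 3 is certain if the first two are alike and both seen: p²/3. Position 4 is certain if both patients of the repeated label are seen: p². The mean is (p²/3 + p²)/4 = p²/3. Best-guess success by position is 1/2; 1/2 + p/6; 2/3 − (1−p)²/6; and 2/3 + p³/3 − (1−p)³/6.

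| p (assumed) | Certain share, p²/3 | Mean best-guess success |
|---|---|---|
| 1 (per-hospital list, or all seen) | 33.3% | 71% |
| 0.8 | 21.3% | 66% |
| 1/2 (two equal sites) | 8.3% | 60% |
| 1/3 (three) | 3.7% | 57% |
| 1/4 (four) | 2.1% | 55% |
| 1/5 (five) | 1.3% | 54% |

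**Alternatives, again with full sight.** A fixed, known block of 2m has a certain share of 1/(m+1): 1/5 = 20% for blocks of 8 and 1/7 = 14.3% for blocks of 12, with best-guess success of 66.6% and 64.3%. For randomly varied sizes, 3,000 lists of 80 were simulated against an observer who knows the possible sizes, equally likely, but not their order. The certain share was about 7.5% for sizes 4 and 8, and about 2.8% for 4, 8 and 12.

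**The case against.** The strongest reply is that one third is a ceiling, not a property of this trial. It needs sight of every earlier Arm 2 allocation in the block and knowledge of where the block starts, whereas the plan discloses only the size. A single website serving several hospitals, with no stated stratification, fits a central list at least as well as per-hospital lists, and then the certain share may be only a few percent. All of this stands, and the figure is given here as an upper bound with a range.

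Other tempting readings are also unsupported:

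- **That the spironolactone factor is unmasked to staff.** Section 3.1 declares the treating physician and investigator blinded. That this is hard to maintain without a placebo is a fair inference, not a documented fact.
- **That one busy hospital would see most of a central sequence.** The plan gives neither the number of sites nor their recruitment shares.
- **That the analysis could not repair any bias.** Section 3.4 collects electrolytes, creatinine and cystatin C at randomization. Adjustment could help in part, but not for unmeasured reasons for selection, and none is planned.
- **That the allocation is shown before the patient is registered.** The plan does not say so.
- **That the sodium end-point of Arm 1 is affected.** Knowledge of Arm 2 labels alone leaves Arm 1 at 50%.

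Enrolment is also meant to be consecutive, within 8 h of diagnosis (section 3.2.1), and is closed to patients already given a set amount of loop diuretic during the admission (section 3.2.2). This leaves little room to time an enrolment. It does not prevent a patient from being passed over, and no screening log is described.

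**Conclusion.** The point holds as an avoidable weakness in allocation concealment for Arm 2; the documents do not show that bias has occurred or will occur. With a fixed, published block of 4, the certain share of Arm 2 allocations is at most one third and best-guess success at most 71%. For a central list the certain share is p²/3, about 1% to 8% over an assumed five to two equal sites and 21% if staff see 80% of the list. All these figures assume that block starts are known. Where the trial lies in this range cannot be settled from the plan, because it is silent on the structure of the list and on how staff blinding is kept. Confidence is moderate. The change is worth making because it costs almost nothing and works across the whole range.

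**What to change.** Have the website algorithm draw block sizes at random from multiples of four, for example 4 and 8, or 4, 8 and 12. Keep the sizes out of any document that screening staff can read. Even for an observer who sees every earlier Arm 2 allocation, this lowers the certain share from 33% to about 7.5% or 2.8%. Guessing better than chance is reduced rather than abolished.

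Add short statements to section 3.1 on whether the list is central or per hospital, and on how the treating physician, the investigator and the screening staff are kept from learning Arm 2 allocations.

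The cost is a parameter change in the randomization program and a few lines of text. The downside is a slightly larger possible imbalance if recruitment stops mid-block. Within an unfinished block, the two Arm 2 levels can differ by at most half the block size: 2 patients for a block of 4, 4 for a block of 8 and 6 for a block of 12, against 40 planned per level. With per-hospital lists this could arise once in each hospital.
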